#### Baseline staging:

- Calculate P&R model-derived risk for the following prodromal AD stages(CN, SCD, MCI Stage I, etc.).
- Assign participants to CN and MCI risk strata (low, average, high PRS or four quantile-based categories)

Cerebrospinal fluid (CSF):

This protocol does not require any research-mandated lumbar punctures or CSF collection. If a participant undergoes lumbar puncture purely for clinical reasons outside the study (e.g., to resolve diagnostic uncertainty as part of routine care), and if the clinical team and participant agree, residual CSF may be shared with the study for exploratory biomarker assays under a separate biobanking consent. No lumbar puncture will be performed solely for research purposes, and participation in the study is not contingent on undergoing a lumbar puncture.

### **4.3 Follow-up visits (Months 6, 12, 18, 24)**

At each follow-up:

- Interval history, adverse events, and medication changes.
- CDR (global and CDR-SB) and a selected neuropsychological battery to detect MCI criteria and progression.
- Repeat digital cognitive assessments (Punto Health).
- Blood collection (venous and/or fingerstick) for plasma pTau217 and other biomarkers, plus proteomic/methylome panels as budget permits.
- Update on digital monitoring adherence and troubleshooting of devices.
- EEG and retinal imaging at selected visits (e.g., baseline and Month 24 for all, optional intermediate visits in a subset depending on resources).
- Additional imaging (MRI or amyloid PET) only when clinically indicated or available as standard-of-care.

Trigger-based assessments:

- If continuous monitoring or participant self-report suggests cognitive decline (e.g., sustained changes in speech patterns, activity, or sleep; decline in digital cognitive tasks), a targeted evaluation will be scheduled, including repeat CDR, brief neuropsychological testing, and biomarker sampling when feasible.

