### Secondary aims

3. Compare the prognostic performance of the P&R model with simpler baseline models (e.g., APOE + PRS only, or clinical + cognitive only) for predicting CN  $\rightarrow$  pTau217-positive MCI conversion over 24 months.
4. Estimate, with appropriate uncertainty, short-term (2–5-year) conversion probabilities derived from the P&R model and explore how these inform projected longer-term (up to ten-year) risk in this population, recognizing that extrapolations will be preliminary and supported by external cohorts.
5. Evaluate the practical scalability and relative cost of alternative sampling and visit strategies, including venous versus capillary (fingerstick) blood collection and varying degrees of in-clinic versus remote assessment, using simple per-participant and per-conversion cost summaries.
6. Assess the incremental predictive value, beyond the core P&R model, of selected digital and wearable measures (e.g., Oura-derived sleep and activity metrics, brief speech, and digital cognitive features) for detecting CN  $\rightarrow$  MCI conversion events.

7. Determine the relationship between an Oura Ring–based exposome risk score and proteogenomic risk scores and cognitive-functional measures.

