## **4. Study Procedures**

### **4.1 Schedule of events**

Each participant will have:

- Baseline visit (Month 0) with full assessments and biospecimen collection.
- pTau217 MCI positive subject will be referred to a Neurologist while the main CN group will have:

- Follow up visits on Months 6, 12, 18, and 24 ( $\pm 2$  months) with repeat biospecimens, neurocognitive testing, and safety review.
- Continuous or frequent digital monitoring (passive and active) throughout the 24 months. (or until they turn MCI positive)
- Optional "triggered" visits or remote assessments in response to signs of cognitive or functional decline detected by digital systems, participant report, or clinical assessment. (If blood biomarkers become positive then these subjects will be referred to a Neurologist and discharged from the study.

Total biospecimen collections per participant: 1 at baseline + 4 follow-ups = 5 (if they do not convert to MCI positive)

Biofluid: venipuncture and/or capillary collections every 6 months for 2 years.

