### **4.4 Biospecimen handling and storage.**

Informed consent	X						
Inclusion / exclusion criteria	X	X	X	X	X	X	X
Medical / neurological / psychiatric history	X						
Medication review	X	X	X	X	X	X	X
Physical and neurologic examination		X				X	O
Vital signs (clinic or wearable)	X	X	X	X	X	X	X
Documentation of prior ApoE genotype and WGS / array data	X						
PRS calculation & stratification (once data available)		X					

CDR (global and CDR-SB, no-informant version)		X	X	X	X	X	X
Digital cognitive battery and brief speech measures (Punto Health)		X	X	X	X	X	O
BIOFLUID COLLECTION (core)							
Venous or capillary blood (pTau217 + core panel for P&R model)		X	X	X	X	X	X
Additional plasma markers (extended AD panel, as budget permits)		O	O	O	O	O	O
Blood methylome / other discovery omics (sub-cohort only)		O	O	O	O	O	O

Clinical labs from EMR or PCP (CBC, CMP, etc.)	0	0	0	0	0	0	0
CSF collection (clinically indicated lumbar puncture only)		0					0
Resting / provoked EEG (sub-cohort, if available clinically)		0				0	0
Retinal hyperspectral imaging (if available clinically)		0				0	0
Amyloid PET (standard-of-care only, if ordered by clinician)		0	0	0	0	0	0
MRI / structural imaging (standard-of-care only)		0	0	0	0	0	0

Digital devices and monitoring							
Oura Ring data linkage / device confirmation	O	X					
Continuous Oura monitoring (sleep, activity, HR metrics)		X	X	X	X	X	X
Digital monitoring adherence check (Oura + cognitive app)		X	X	X	X	X	X
Risk score calculation and staging							
Calculate P&R risk score and risk level		X	X	X	X	X	X
Update CN / SCD / MCI Stage I status and event determination		X	X	X	X	X	X

† Triggered visits or remote assessments will occur when digital monitoring, participant report, or clinical assessment suggests possible cognitive decline or functional change; they may include focused cognitive testing and repeat blood sampling for key biomarkers (e.g., pTau217) and will prompt referral to a neurologist if criteria for MCI with positive biomarkers are met.

---

Notes:

- Total in-clinic visits: 5 required (Baseline + 4 follow-ups at 6, 12, 18, 24 months), plus optional triggered visits.
- Total biospecimen collections: 5 venipuncture/capillary sessions minimum (Baseline + 4 follow-ups), plus optional triggered samples

Duration of participation: 24 months from baseline with continuous remote monitoring

---

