### 5.2 Secondary outcomes

- Time to conversion from CN to MCI Stage I (regardless of pTau217 status) and from CN to pTau217-positive status (biomarker conversion).

- Estimated ten-year conversion rates from CN to MCI Stage I, extrapolating from observed two-year data using survival/hazard modeling informed by external cohorts.
  - Hazard ratios for LOAD associated with P&R model-derived risk scores, PRS categories, and biomarker trajectories.
  - Cost per participant and per conversion event detected for different sampling strategies (fingerstick vs venous; frequency of in-person visits vs reliance on digital monitoring).
  - Incremental predictive value (AUC-ROC, net reclassification improvement) of continuous digital monitoring features (smell, location, activity, speech, EEG, sleep) beyond traditional risk factors and biomarkers.
- 

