## 6. Statistical Considerations

### 6.1 General approach

Data analyses will be primarily exploratory and hypothesis-generating given the FIH nature and modest sample size, but key performance metrics (e.g., AUC-ROC) will be estimated with confidence intervals. Observational protocol templates recommend prespecifying primary analyses and sensitivity analyses for observational cohorts.

Analyses:

- Compute AUC-ROC for the P&R model and alternative models for predicting conversion to pTau217-positive MCI Stage I within 24 months.
- Compare AUC-ROC across models (proteogenomic vs proteo-methylome-genomic) using DeLong's test or similar.
- Use Cox proportional hazards models to estimate hazard ratios for time to conversion as a function of baseline P&R risk, PRS, ApoE4 dose, and biomarker levels.
- Use logistic regression and time-dependent ROC analyses for binary conversion endpoints over fixed time horizons.
- Incorporate digital monitoring variables as covariates and evaluate incremental predictive performance.
- For cost-effectiveness, compare costs and detection yield of different biospecimen and monitoring strategies using simple decision-analytic models (incremental cost per correctly predicted conversion).

Missing data will be handled using appropriate methods (e.g., multiple imputations, mixed-effects models) depending on pattern and mechanism of missingness. Sensitivity analyses will evaluate robustness of results to missing data assumptions.

---

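### The digital features tested for added value also trigger extra endpoint assessments, and the stated NRI measure and conflicting comparators can further mislead on Aim 6

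*Protocol*

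**What the plan says.** **Trigger.** Section 4.3 provides that, after digital signals such as "sustained changes in speech patterns, activity, or sleep; decline in digital cognitive tasks), a targeted evaluation will be scheduled", with repeat CDR, brief testing and biomarker sampling when feasible. Section 4.1 describes optional visits "in response to signs of cognitive or functional decline detected by digital systems, participant report, or clinical assessment", so self-report and clinical judgement are triggers too.

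**Events at triggered visits.** In the schedule table (under section 4.4), the row "Update CN / SCD / MCI Stage I status and event determination" is marked six times from baseline on. Baseline plus four follow-ups makes five, so the sixth mark is read as the triggered visit described in the table's footnote. Everyone is also assessed at the scheduled visits: "Follow up visits on Months 6, 12, 18, and 24".

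**Exit.** Section 4.1, on triggered visits: "If blood biomarkers become positive then these subjects will be referred to a Neurologist and discharged from the study".

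**Analysis.** Aim 6 is to "Assess the incremental predictive value, beyond the core P&R model, of selected digital and wearable measures"; its examples are Oura sleep and activity metrics, brief speech and digital cognitive features. Section 5.2 lists "Incremental predictive value (AUC-ROC, net reclassification improvement) of continuous digital monitoring features (smell, location, activity, speech, EEG, sleep) beyond traditional risk factors and biomarkers". Section 6.1 says: "Incorporate digital monitoring variables as covariates and evaluate incremental predictive performance".

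**The concern.** The features under test help decide who is examined for the endpoint, how often and when. A participant whose sleep or speech score drifts by chance gets more opportunities to be called converted, and an earlier date if truly converting. Because the features are recorded continuously and no landmark is set, values up to the triggered diagnosis are not excluded from predicting that diagnosis.

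Two further problems lie in how added value is measured. NRI is a stated measure, and it is prone to false positives when new covariates are fitted and assessed in the same small data set. The comparator also conflicts: added value over the core P&R model (Aim 6) is a different question from added value over traditional risk factors and biomarkers (section 5.2).

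At stake is a named secondary aim. A reported gain for digital monitoring could partly reflect extra looking and a poorly behaved statistic.

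**Working it through.** The protocol states no conversion rate, event count or precision target, so there is no figure of its own to reproduce.

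**1. Overlap of triggers and predictors**

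| Feature | Trigger example (4.3) | Tested (Aim 6 or 5.2) |
|---|---|---|
| Speech | yes | both |
| Activity | yes | both |
| Sleep | yes | both |
| Digital cognition | yes | Aim 6 |
| Smell, location, EEG | not named | 5.2 |

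Every named digital trigger is also a tested predictor.

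**2. Expected events (assumed rates)**

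Events = N × [1 − (1 − r)²]. N is 90 (section 2.1, an upper limit) or 100 (section 3.2); r is assumed.

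| r per year | N = 90 | N = 100 |
|---|---|---|
| 2% | 3.6 | 4.0 |
| 5% | 8.8 | 9.8 |
| 10% | 17.1 | 19.0 |

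The range is about 4 to 19 events.

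**3. Size of the trigger effect**

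Take a flag unrelated to disease. Let p be true 24-month conversion and f the false-conversion rate per assessment, with four scheduled assessments for all and two extra for flagged participants (p, f and the two visits are assumptions). With true converters all detected,

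ratio = [1 − (1 − p)(1 − f)⁶] / [1 − (1 − p)(1 − f)⁴].

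| f | p = 8% | p = 10% |
|---|---|---|
| 1% | 0.1338 / 0.1163 = 1.15 | 0.1527 / 0.1355 = 1.13 |
| 2% | 0.1850 / 0.1514 = 1.22 | 0.2027 / 0.1699 = 1.19 |
| 3% | 0.2337 / 0.1855 = 1.26 | 0.2503 / 0.2032 = 1.23 |

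Simulation gives about 1.14-1.25. At f = 1% with two extra visits, the noise feature's AUC is 0.51-0.52. With perfect assessment (f = 0) there is no effect on 24-month status, only on the date of detection. With per-visit sensitivity of 0.5-0.7 and no false calls, the ratio is 1.03-1.14 over one to four extra visits.

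**4. Behaviour of NRI if fitting and evaluation share the data**

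Null simulation: n = 100; 5, 10 or 19 events; an informative core score plus noise features, refitted by logistic regression; tests at 5%.

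| Noise features | Category-free NRI test rejects | Likelihood-ratio test rejects |
|---|---|---|
| 1 | 7-8% | 5-9% |
| 3 | 27-33% | 5-9% |
| 6 | 57-63% | 5-9% |

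(The 5-9% is the range over all settings.) With 10 events and a core AUC of 0.80, the mean same-data AUC gain from noise is 0.011, 0.032 and 0.061 for one, three and six features. In independent data it is −0.012, −0.033 and −0.059. Category-free NRI stays positive even there (0.05, 0.10, 0.14), so validation alone does not rescue it.

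**5. Why scheduled-visit counting alone is not a remedy**

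Participants found biomarker-positive at a triggered visit are discharged and have no later scheduled visit. Counting only scheduled-visit events would drop these converters, nearly all from the flagged group. Simulated with a noise flag and discharge, the flagged-to-unflagged ratio falls to 0.79-0.85: a useless feature looks protective.

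**The case against.** A reader might infer that the protocol plans an in-sample analysis on about 10 events and that useless features will therefore look predictive. The documents do not support that. No event count is given; 10 corresponds to an assumed rate near 5% per year. Section 6.1 does not say that performance is measured in the fitting data. Optimism correction, feature windows and the NRI variant could sit in an analysis plan that is not shown. With one digital summary the NRI test is close to nominal, and Aim 6 speaks of selected measures. EEG is for a sub-cohort only, so six covariates in everyone is an upper case. If DeLong's test were used for these comparisons (section 6.1 names it for another pair of models), it would reject for noise in under 1%, about 2% and 11-14% of trials with one, three and six features.

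A reader might also put the trigger effect at 1.4-1.5. That factor, [1 − (1 − f)⁶] / [1 − (1 − f)⁴] for f of 1-5%, concerns false conversions alone. Over all conversions the effect is smaller, because everyone is assessed every six months. The endpoint also requires both MCI criteria and pTau217 above a cut-off, so false calls may be rarer than assumed.

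Finally, section 6.1 calls the analyses primarily exploratory.

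These points limit the size and make the overfitting part conditional. They do not remove the link between tested features and endpoint assessment, the choice of NRI or the conflicting comparators, all of which are in the text.

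**Conclusion.** The point holds in a limited form. The firm part rests on the text: digital changes prompt extra assessments at which conversion can be declared, the same features are then tested as predictors, and no time separation is set. The resulting bias favours the digital features and is modest: about 1.14-1.25 times the conversions by 24 months for a noise flag, given two extra visits and a 1-3% false-call rate, plus earlier detection in time-to-event analyses.

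The NRI part is conditional. If three to six digital covariates are fitted and evaluated in the same data, false-positive rates are about 27-63%; with one they are 7-8%. It does not follow that Aim 6 must report a spurious gain.

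The difference in base model between Aim 6 and section 5.2 is a plain inconsistency. The changes should be made before the analysis is fixed.

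**What to change.** For Aim 6 and the matching outcome in section 5.2:

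1. Take digital features from a fixed early window, for example baseline to Month 6, and analyse conversions after that landmark.
2. Keep conversions found at triggered visits, dated to the next scheduled visit. This removes the earlier-detection advantage without losing discharged participants.
3. Add a sensitivity analysis that censors participants at a triggered conversion, and report how many conversions were first found at triggered visits. The main analysis can still carry extra false calls from later triggers, whereas censoring removes events mainly from flagged participants and so errs the other way. Read the two together.
4. Replace NRI with a likelihood-ratio or permutation test of one or a few prespecified digital summaries added to the locked P&R linear predictor. Report the optimism-corrected AUC change with a confidence interval.
5. Name the core P&R model as the base in both places.

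**Cost.** The change is to analysis wording, plus recording whether each conversion was first found at a scheduled or triggered visit. Conversions before the landmark are not used for Aim 6: at a constant rate, a Month 6 landmark leaves 18/24 of follow-up, so 3.6-19.0 events become roughly 2.7-14.3. Apparent gains will shrink.

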### **4.4 Biospecimen handling and storage.**

Informed consent	X						
Inclusion / exclusion criteria	X	X	X	X	X	X	X
Medical / neurological / psychiatric history	X						
Medication review	X	X	X	X	X	X	X
Physical and neurologic examination		X				X	O
Vital signs (clinic or wearable)	X	X	X	X	X	X	X
Documentation of prior ApoE genotype and WGS / array data	X						
PRS calculation & stratification (once data available)		X					

CDR (global and CDR-SB, no-informant version)		X	X	X	X	X	X
Digital cognitive battery and brief speech measures (Punto Health)		X	X	X	X	X	O
BIOFLUID COLLECTION (core)							
Venous or capillary blood (pTau217 + core panel for P&R model)		X	X	X	X	X	X
Additional plasma markers (extended AD panel, as budget permits)		O	O	O	O	O	O
Blood methylome / other discovery omics (sub-cohort only)		O	O	O	O	O	O

Clinical labs from EMR or PCP (CBC, CMP, etc.)	0	0	0	0	0	0	0
CSF collection (clinically indicated lumbar puncture only)		0					0
Resting / provoked EEG (sub-cohort, if available clinically)		0				0	0
Retinal hyperspectral imaging (if available clinically)		0				0	0
Amyloid PET (standard-of-care only, if ordered by clinician)		0	0	0	0	0	0
MRI / structural imaging (standard-of-care only)		0	0	0	0	0	0

Digital devices and monitoring							
Oura Ring data linkage / device confirmation	O	X					
Continuous Oura monitoring (sleep, activity, HR metrics)		X	X	X	X	X	X
Digital monitoring adherence check (Oura + cognitive app)		X	X	X	X	X	X
Risk score calculation and staging							
Calculate P&R risk score and risk level		X	X	X	X	X	X
Update CN / SCD / MCI Stage I status and event determination		X	X	X	X	X	X

† Triggered visits or remote assessments will occur when digital monitoring, participant report, or clinical assessment suggests possible cognitive decline or functional change; they may include focused cognitive testing and repeat blood sampling for key biomarkers (e.g., pTau217) and will prompt referral to a neurologist if criteria for MCI with positive biomarkers are met.

---

Notes:

- Total in-clinic visits: 5 required (Baseline + 4 follow-ups at 6, 12, 18, 24 months), plus optional triggered visits.
- Total biospecimen collections: 5 venipuncture/capillary sessions minimum (Baseline + 4 follow-ups), plus optional triggered samples

Duration of participation: 24 months from baseline with continuous remote monitoring

---

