- Define 4 Categories CN individuals whose predicted 2–5-year conversion risk to MCI lies above a prespecified percentile cut-off (25 % lowest risk quartile, 25% next to lowest risk quartile, 25% next to highest risk quartile, and 25% highest risk quartile)
- Define 4 Categories of SCD whose predicted 2–5-year conversion risk to MCI lies above a prespecified percentile cut-off (25 % lowest risk quartile, 25% next to lowest risk quartile, 25% next to highest risk quartile, and 25% highest risk quartile)
- Estimate annual conversion rates within these model-defined groups (CN vs SCD), which are expected to differ by several-fold based on prior work showing strong stratification by proteomic, cognitive assessment, and multi-omic risk scores.

These estimated event rates (number of pTau217 positive MCI conversions per patient-years) are then used to justify the future FIH longitudinal sample size and follow-up duration described in Sections 1.2 and 3.2.

Fixed model for the FIH cohort

Once selected, the P & R model will be locked (fixed coefficients and included markers) before analysis of the FIH cohort. For each enrolled participant, we will calculate the P & R risk score at baseline and use it to:

- Assign CN participants to 4 CN Risk Levels and 4 SCD Risk Levels (per the thresholds derived above).
  - Generate individual predicted hazards of conversion for comparison with observed events (primary and secondary analyses).  
The FIH study itself is thus a prospective validation of a pre-specified P & R model developed entirely from existing data.
- 

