#### **3.3 Inclusion criteria**

- Age  $\geq 55$  years at enrollment.

- At least one ApoE4 allele documented by prior testing (e.g., prior genetic panel, research cohort genotyping, clinical ApoE testing).
- Whole-genome sequencing (WGS) data previously completed and participants willing to provide existing WGS data files (e.g., VCF, FASTQ, or equivalent) to the study team for polygenic risk score (PRS) calculation.
- If WGS is not available but targeted genotyping arrays covering AD risk loci are available, participants willing to provide these data for PRS calculation (the study will assess feasibility of array-based PRS on a case-by-case basis)
- 
- Cognitively normal or very mildly impaired at baseline, defined by:
  - The Ponto Test and digital cognitive assessment equivalent of a Global CDR 0 or 0.5, and no clinical diagnosis of dementia.
  - For CN and SCD, P&R model staging criteria will be applied (combining PRS, biomarker, and cognitive data).
- Subjects that do not currently qualify for MCI status. (ie with the equivalent of a g CDR 0.5 - 1.0 , and plasma or CSF pTau217 level above a validated cut-off for AD-MCI pathology.
- Ability to provide informed consent and to comply with study procedures.
- Willingness to wear/keep digital devices for continuous monitoring (e.g., smartphone app, wearable sensors, sleep device).
- Note on genetic testing: This protocol does not perform ApoE genotyping or whole-genome sequencing as a research procedure. Eligible participants must already have these tests completed through prior clinical care, prior research studies, or commercial/direct-to-consumer services, and must be willing to share the results and raw genomic data files with this study. Screening will confirm that (a) prior ApoE genotype shows at least one  $\epsilon 4$  allele, and (b) WGS or suitable array data exist and can be obtained for PRS calculation. Individuals without documented ApoE4 carrier status or without available genomic data for PRS are ineligible for this protocol.

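### Nothing in the protocol keeps those who call conversion events from seeing the P&R score being validated, which leaves the primary AUC open to a modest upward bias

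*Protocol*

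**What the plan says.** The schedule of events (the table under protocol section 4.4) contains a block headed "Risk score calculation and staging". It has two rows, "Calculate P&R risk score and risk level" and "Update CN / SCD / MCI Stage I status and event determination". Both are marked as required in the same six columns, which correspond to baseline, Months 6, 12, 18 and 24, and triggered visits.

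Section 2.2 locks the model before the cohort is analysed and says that "we will calculate the P & R risk score at baseline", both to assign risk levels and to compare predicted with observed conversion. Primary aim 1 in 1.2 is to validate that fixed model's discrimination over 24 months.

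Section 5.1 defines the event by two requirements. The first is a clinical diagnosis of MCI due to AD on consensus criteria, with CDR global given only as approximately 0.5 and CDR-SB given as a verbal range. The second is plasma pTau217 above a validated cut-off. The P&R score is not part of this definition. Section 5.2 adds time to MCI Stage I irrespective of pTau217.

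The P&R model is also mentioned in baseline staging. Section 3.3 says "For CN and SCD, P&R model staging criteria will be applied (combining PRS, biomarker, and cognitive data", and 4.2 lists "Calculate P&R model-derived risk for the following prodromal AD stages(CN, SCD, MCI Stage I, etc".

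No section says who calculates the score, who calls events, in what order, or whether the second person may see the work of the first. There is no provision for blinded or independent adjudication.

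**The concern.** In a validation study the outcome must be settled independently of the predictor. If an assessor facing a borderline case knows that the participant is in the top risk level, the case is more likely to be called MCI. The endpoint then partly reflects the predictor, and the AUC rises without any gain in real discrimination.

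This protocol makes that possible because it schedules score and event call together, as one activity, and sets no barrier between them. Primary aim 1 rests on the resulting AUC. A statistical analysis plan cannot repair this afterwards, because a call made with the score in view cannot be remade blind.

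**Working it through.** **Reading the text.** The argument needs three facts, and all are in the protocol.
1. Score and event call coincide at every visit (4.4).
2. Part of the event call is judgement (5.1, clinical half).
3. No rule separates the two (absent from 2.2, 4.2 to 4.4, 5.1, 6.1 and 10).

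The score under validation is the baseline one (2.2). Bias therefore arises through knowledge of the baseline score or level, or of a follow-up score correlated with it.

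**What the protocol supplies for a size.** It gives no conversion rate, event count, target AUC or share of borderline cases, so there is no stated figure to reproduce. The only input from the document is the sample size: up to 90 in 2.1 (3.2 says 100). Everything else below is assumed.

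**Small-sample illustration.** Assumptions: 90 participants; 9 true converters (10%); normal scores with the converters' mean shifted by √2·Φ⁻¹(AUC). Four, 8 or 12 non-converters are diagnostically borderline. With the score visible, a borderline case is called an event only if its score is in the top quartile. With the score hidden, 25% of borderline cases are called events at random. The table shows the mean AUC over 4,000 replicates at a true AUC of 0.70.

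| Borderline cases | Score visible | Shift from 0.70 | Score hidden |
|---|---|---|---|
| 4 | 0.720 | +0.020 | 0.681 |
| 8 | 0.739 | +0.039 | 0.664 |
| 12 | 0.756 | +0.056 | 0.652 |

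Hand check for 8 cases: on average about 1.84 of them lie in the top quartile. A top-quartile score has a mean percentile of 0.875. The apparent AUC is then roughly (9 × 0.70 + 1.84 × 0.875) / (9 + 1.84) = (6.30 + 1.61) / 10.84 = 0.73. The simulated value is slightly higher because those high scorers also leave the non-event group.

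With 8 borderline cases and a weaker score, the shift grows. A true AUC of 0.60 appears as 0.66 (+0.06), and a useless score at 0.50 appears as 0.58 (+0.08). About two extra event calls are enough in each case.

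**Large-sample check of direction.** One million simulated subjects, 10% conversion, 10% of participants borderline, correlation between baseline and visit score set at 0.7 to 1.0:
- true AUC 0.50 appears as 0.56 to 0.59;
- true AUC 0.65 appears as 0.68 to 0.71;
- true AUC 0.75 appears as 0.76 to 0.79.

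The shift was upward in every setting tried (conversion 5 to 15%, borderline share 5 to 20%).

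**Against sampling error.** The Hanley-McNeil variance is [A(1−A) + (n₁−1)(Q₁−A²) + (n₀−1)(Q₂−A²)] / (n₁n₀), with Q₁ = A/(2−A) and Q₂ = 2A²/(1+A). For A = 0.70, n₁ = 9 and n₀ = 81, Q₁ = 0.538 and Q₂ = 0.576. The variance is (0.210 + 0.388 + 6.918) / 729 = 0.0103, so SE ≈ 0.10. A bias of 0.04 is about 0.4 SE.

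**The case against.** The strongest reply is that the event definition in 5.1 does not use the P&R score, and that adjacent rows in a table show what is scheduled, not who sees it. That is right. The text supports only that assessors could see the score, not that they would. A separate manual might restrict access, but the protocol does not say so.

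The second reply is that the pTau217 criterion is an assay threshold, so a tipped clinical call counts only if the assay is also positive. This stands as a limit. If half of 8 borderline cases failed the assay, the 4-case figure of +0.02 would apply. The 5.2 outcome regardless of pTau217 has no such limit.

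The third reply is that the bias is small against an SE of about 0.10, in a study that 6.1 calls mainly exploratory. That is also fair. But the bias has one direction, and the confidence interval does not reflect it.

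Some stronger readings are tempting, and the documents do not support them:
- *P&R staging formally feeds the endpoint.* Sections 3.3 and 4.2 use it at baseline only, and 5.1 does not name it.
- *Recalculated scores serve no analysis.* Section 2.1 foresees refining the model, 5.2 lists hazard ratios for P&R scores and biomarker trajectories, and 6.1 lists time-dependent ROC. Repeat scores could serve any of these.
- *Follow-up scores would exist for some participants only.* Section 4.3 does say "plus proteomic/methylome panels as budget permits", but the 4.4 table marks blood for pTau217 and the core P&R panel as required at every visit. At most the two places need reconciling.
- *The bias is the gap between 0.74 and 0.66.* The lower figure is itself pulled down by random misclassification. Measured against the truth, the bias is about 0.04.

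**Conclusion.** The point holds as a gap in the protocol. Score and event determination are scheduled together, the clinical half of the endpoint involves judgement, and nothing keeps the score from those who make the call. The primary AUC is therefore open to upward bias.

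The direction is clear, but the size cannot be derived from the documents. Under the assumed inputs (90 participants, 9 converters, 4 to 8 borderline non-converters called by top score quartile, true AUC 0.70) it is about +0.02 to +0.04. It is larger if the true AUC is lower, and smaller if the assay threshold screens out tipped cases. This is an inexpensive improvement worth making before enrolment. It does not show that the study's result will be wrong.

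A separate overlap would remain even with blinding: under 2.2 the score itself contains pTau217 and cognitive-functional measures, the same domains that define the event.

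**What to change.** 1. In 5.1, state that event determination uses only the 5.1 criteria and is recorded without access to any P&R score or risk level, the baseline one included.
2. In the 4.4 table, change the P&R row so that follow-up scores are computed in one batch after event status is locked. Restricting the row to baseline would not be enough by itself, because the baseline score is the one under validation and would stay visible.
3. In 6.1, state that the primary AUC uses the locked baseline score. At present only the Cox analysis there is tied explicitly to baseline P&R risk.

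The rule covers the composite score and level. It cannot hide plasma pTau217, which 5.1 itself requires. Referral under the 4.4 table footnote depends on MCI criteria with positive biomarkers, not on the P&R score, so it is unaffected.

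The cost is a schedule edit and two sentences, with no added staff, visits or assays. The downside is that no real-time risk update is available during follow-up.
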